4.1.1 Figure 2. Conceptual Model

4.2 Naltrexone (NTX) and Extended-Release Naltrexone (XR-NTX)

NTX is a potent opioid antagonist with high affinity for the mu-opioid receptor. In the U.S., it is approved for use in treating opioid dependence and alcohol dependence. It is highly efficacious in preventing relapse to opioid dependence provided that it is taken as prescribed, but adherence with oral naltrexone is problematic and leads to extremely high dropout rates, with the occasional exception of treatment in criminal justice and other settings where relapse may be linked to severe adverse consequences [96-98]. This has led to intensive efforts – including NIDA- and NIAAA-funded grants to small businesses – to develop long-acting naltrexone preparations that can be administered as an injection or placed as an implant once per month or less frequently [99, 100].

XR-NTX (Vivitrol®, NTX-containing polylactide-co-glycolide [PLG] biodegradable sterile microspheres suspended in a diluent) is delivered by monthly injection into the muscles of the upper outer quadrant of the buttock. Each vial of microspheres contains 380 mg NTX which are suspended by adding a diluent that comes with the product and shaking for about a minute prior to injection of the full (less dead-space) content of the vial. Plasma concentrations of NTX and 6-beta-naltrexol (its main active metabolite) after a single XR-NTX injection are detectable for at least 30 days. Consistent with this, in human laboratory studies with Vivitrol® and Depotrex®, an essentially complete blockade of opioid agonist effects is seen for 30 days [101, 102]. To maintain blockade beyond 30 days, XR-NTX must be re-administered. Long-term use of NTX and XR-NTX is not associated with tolerance, dependence, addiction or withdrawal on discontinuation. NTX and XR-NTX will, however, precipitate withdrawal in individuals physiologically dependent on opioids and decrease opioid tolerance.

As a consequence of its extended duration of action and assured treatment adherence, XR-NTX may dramatically and favorably alter the limited effectiveness profile associated with orally administered NTX. By ensuring 30-day medication adherence with a single injection, and thereby establishing a ~30 day mu-opioid antagonist blockade, the likelihood of an individual re-establishing opioid dependence during this period is very low. Two clinical trials support efficacy for XR-NTX preparations compared to placebo injections [54, 55].

The 2006 Comer et al. study [54] was a proof-of-concept, 2-month randomized, placebo-controlled trial with a subcutaneously administered product (Depotrex®, Bitek Inc.), and showed that long-acting injectable naltrexone in conjunction with outpatient counseling produced superior treatment retention to placebo, providing evidence of the feasibility, efficacy, and tolerability of long-lasting antagonist treatments for opioid dependence.

The Krupitsky et al. study [55] was conducted in 2008 and 2009 in 13 sites in Russia, and was sponsored by the manufacturer, Alkermes, Inc. Following inpatient detoxification, 250 opioid-dependent participants were randomized to XR-NTX or placebo, double-blind monthly injections,

for 6-months, during which all participants received outpatient counseling. The percent of opioid abstinent weeks, by weekly urine toxicology, was the primary outcome. A response profile analysis compared the cumulative percent of participants at each level of the outcome (percent opioid-free weeks) between the active XR-NTX and placebo conditions. The difference between the response profiles was significant ($p < .0002$), with the median participant on XR-NTX having 90% abstinent weeks compared to 35% abstinent weeks for the median participant on placebo. Total abstinence (100% opioid-free weeks) was reported in 45 (35.7%) participants in the XR-NTX group versus 28 (22.6%) participants in placebo group ($p < .03$). Retention in treatment for the full 6 months was 53% on XR-NTX, compared to 38% on placebo ($p < .02$). The 6-month retention rate in the 50% range is similar to that observed in clinical trials of buprenorphine [103]. Participants treated with XR-NTX showed an approximately 50% sustained reduction in craving compared to no change in craving in the placebo group ($p < .005$). XR-NTX was generally well tolerated. Data from this trial supported Alkermes' supplemental NDA for treatment of opioid dependence.

Prescribing and Safety: Details on XR-NTX prescribing, pharmacokinetics and pharmacodynamics, metabolism and elimination, safety and toxicity are in the XR-NTX package insert.

4.3 Treatment as Usual (TAU)

The current standard of care for treatment of opioid use disorders in HIV clinics is opioid agonist therapy. Recent HIV treatment guidelines recommend office-based BUP/NX or referral for methadone maintenance for HIV-infected patients with opioid use disorders [35, 104]. Through the efforts of the Health Resources and Service Administration (HRSA)-funded Buprenorphine and HIV Evaluation Study (BHIVES) and Substance Abuse and Mental Health Services Administration (SAMHSA)-funded Physician Support Service for Buprenorphine, on-site treatment with office-based buprenorphine is increasingly being offered in HIV clinics. A recent HRSA HIV/AIDS Bureau monograph promotes adoption of office-based buprenorphine in HIV primary care [105]; see Section 4.1 for evidence of effectiveness of methadone and buprenorphine. Office-based BUP/NX, together with referral for methadone maintenance therapy, is now the standard of care for treatment of opioid use disorders in many U.S. HIV clinics [104].

Many HIV clinics in the U.S., including those associated with NIDA CTN nodes, receive Ryan White Care Act funding to provide ancillary services for under-insured and uninsured Persons Living with HIV/AIDS (PLWHA). These services typically include on-site case managers, social workers, and substance use counselors who provide critical treatment, referral, and support services for HIV-infected patients with substance use disorders. The site selection process will include a thorough review of existing treatment services.

PRELIMINARY DATA: CTN-0055 CHOICES Pilot: The CTN-0055 CHOICES pilot study tested patient and provider acceptability and feasibility of XR-NTX versus TAU for treatment of opioid and/or alcohol use disorder at two HIV clinic pilot sites (St. Paul's Hospital, Vancouver, B.C. and Core Center, Chicago, IL). Participants were enrolled without regard to baseline HIV viral suppression and opioid and/or alcohol use. The study was designed to continue until 50 participants were enrolled or 12 months elapsed, whichever came first.

Pilot study primary outcomes focused on 5 feasibility primary outcomes, which support the feasibility of a multi-site scale-up trial to assess the effectiveness of XR-NTX in HIV practice:

- 1) **Provider Acceptability.** HIV provider acceptability of XR-NTX was high in a survey of 107 HIV providers – more than 90% reported willingness to refer patients to a clinical trial of XR-NTX [106].

- 2) **Patient Acceptability.** Patients were interested in XR-NTX treatment, as well. The study site in Vancouver, B.C. conducted a survey of 657 persons who inject opioids as part of their site selection application. About half (52%) of the survey participants expressed willingness to receive XR-NTX treatment for opioid use disorder. Daily heroin injection was associated with increased willingness to try XR-NTX (OR 1.53, 95% CI 1.02, 3.12) [107]. Prospective CTN-0055 CHOICES pilot study participants (n=112) were asked about their willingness to participate in a trial of XR-NTX during pre-screening. Ninety-eight percent of prospective participants interested in reducing opioid use (n=60) and 99% of those interested in reducing alcohol use (n=82) were definitely or maybe willing to consider enrolling in a clinical trial of XR-NTX.
- 3) **Randomization Rate.** The CTN-0055 CHOICES pilot study enrolled 51 HIV-infected patients receiving care at two pilot site HIV clinics (mean age 46 years, mean CD4 count 620; 43% women). The trial achieved 155% actual versus expected randomizations, reaching randomization targets 4 months ahead of schedule and enrolling 22 (43%) participants with opioid and 29 (57%) with alcohol as their primary use disorder. Sixteen percent of randomized participants met criteria for *both* opioid and alcohol use disorders. Overall, the pilot study enrolled a mean of 3 participants per month per site.
- 4) **Treatment Initiation.** The majority (68%) of participants assigned to XR-NTX initiated treatment. Five of 12 (42%) participants with any OUD assigned to XR-NTX initiated XR-NTX within 4 weeks of randomization. The CTN-0055 CHOICES pilot study randomized participants prior to detoxification and provides the first benchmark for XR-NTX treatment initiation in community-dwelling people with opioid use disorder. Both of the two clinical trials of XR-NTX for opioid use disorder that led to FDA approval required successful residential detoxification prior to randomization and did not report treatment initiation rates [54, 55]. The CTN-0067 scale-up trial seeks to increase the rate of treatment initiation for participants with OUD with a modified naltrexone induction protocol (Section 9.2.3.1).
- 5) **Treatment Retention.** Of those initiating XR-NTX treatment, 88% were retained on XR-NTX at 16 weeks. Five of 5 (100%) participants with OUD who initiated XR-NTX were retained on XR-NTX at 16 weeks and received all four doses. This exceeds rates reported in the two previously reported clinical trials of XR-NTX for opioid use disorder that observed 68% retention on XR-NTX at 8 weeks in a U.S.-based study [54] and 57.9% at 24 weeks in a study of Russian PWID [55].

The CTN-0055 CHOICES pilot study documents the feasibility of XR-NTX treatment for opioid and/or alcohol use disorder in HIV clinics, but was not powered to assess the effect of XR-NTX on secondary outcomes, including HIV viral suppression and substance use.

Secondary outcomes generated point estimates for a multi-site trial:

- 1) **HIV Viral Suppression**. Overall, 80% of participants had a suppressed viral load (HIV RNA PCR \leq 200 copies/mL) at baseline, and 84% were suppressed at 16 weeks. Among those with OUD, HIV viral suppression improved from 67% to 80% for XR-NTX and 58% to 75% for TAU. Among those with AUD, HIV viral suppression changed from 92% to 82% for XR-NTX and 100% to 100% for TAU. The very high proportion of participants with HIV viral suppression at baseline, particularly among those with only alcohol use disorder, has implications for design of a multi-site non-inferiority trial. Inclusion of participants suppressed at baseline in the scale-up study potentially biases scale-up results toward the alternative (i.e., non-inferiority) hypothesis. In other contexts, non-inferiority trials that cannot distinguish effective from ineffective treatments are said to lack assay sensitivity, jeopardizing the validity of a non-inferior result [108]. Pilot participants with OUD had lower baseline rates of viral suppression and substantial room for improvement. We also anticipate lower baseline HIV viral suppression rates in a scale-up to HIV clinics throughout the U.S., where HIV suppression rates are lower for persons who inject drugs than those observed at the two pilot sites [27, 109, 110]. The CTN-0067 CHOICES scale-up multi-site study seeks to limit the potential for a baseline ceiling effect by excluding participants with only alcohol use disorder and including participants with a non-suppressed HIV viral load at baseline.
- 2) **Substance Use Outcomes**. Among participants with OUD, mean days of opioids use in past 30 days decreased from 19 to 10 for TAU (n=12) and from 18 to 13 for XR-NTX (n=10). Among those with AUD, mean days of drinking to intoxication in the past 30 days decreased from 18 to 7 for TAU (n=11) and 13 to 6 for XR-NTX (n=12).

4.4 Significance to the Field

Expanding HIV providers' armamentarium for treating opioid use disorders and improving viral suppression in HIV-infected patients advances the three major goals of the National HIV/AIDS Strategy for the United States, updated for 2020, including 1) reducing new HIV infections in communities where HIV is most concentrated, 2) increasing access to care and improving health outcomes for people living with HIV, and 3) reducing HIV-related disparities and health inequalities [111]. The primary driver of HIV transmission is HIV viral load. If XR-NTX is effective in increasing viral suppression, fewer new HIV infections will occur among the sexual and drug-using partners of opioid and alcohol dependent individuals [112-114]. The CHOICES scale-up study increases access to care by engaging HIV-infected participants with suboptimal viral suppression to initiate and adhere to ART, and improves health outcomes by increasing viral suppression with resultant improvements in health outcomes and decreased mortality. The CHOICES scale-up study reduces HIV-related disparities and health inequalities by seeking to engage opioid-dependent participants in HIV treatment — a vulnerable population with persistently suboptimal access to high quality HIV care and outcomes, compared with other HIV risk behavior groups. The CHOICES scale-up study also advances the science of opioid use disorders treatment by directly comparing antagonist therapy with TAU in a comparative effectiveness trial to assess the implementation of a novel therapy into HIV clinical practice.

CTN-0067 is well-aligned with three NIH Office of AIDS Research high priority areas for HIV research funding:

- 1) **Reducing Incidence of HIV: developing, testing, and implementing strategies to improve HIV testing and entry into prevention services**. Opioid use disorders are barriers to engagement and retention in HIV care, and consequently HIV-infected patients with

these comorbid disorders are less likely to achieve HIV viral suppression compared with those without. Recruitment strategies will emphasize linkage with local HIV testing outreach efforts affiliated with HIV clinics to encourage entry into HIV treatment of substance users who are newly diagnosed with HIV.

- 2) Next generation of therapies-implementation research to ensure initiation of treatment as soon as diagnosis has been made, retention and engagement in these services, and achievement and maintenance of optimal prevention and treatment responses.
CHOICES scale-up study will provide data on the effect of treating substance abuse on the HIV continuum of care stages: linkage, engagement, retention, and viral suppression. Treatment of underlying opioid use disorders with XR-NTX is likely to increase engagement and retention in HIV care, with consequent HIV viral suppression — the primary outcome for CHOICES scale up. The data gathered by the implementation component of CHOICES scale-up study should facilitate widespread adoption of XR-NTX by HIV clinics following the completion and publication of the study results.
- 3) Research to reduce health disparities in the incidence of new HIV infections and treatment outcomes. *Seventy-three percent* of CHOICES pilot participants were of minority race ethnicity. Scale-up sites will be predominately located in cities with local HIV epidemics that disproportionately affect African-American and Hispanic populations. CTN-0067 CHOICES scale-up study intervention is designed to increase engagement in HIV care leading to ART treatment (a secondary outcome) and HIV viral suppression (the primary outcome) for a predominantly minority race-ethnicity study population. Study outcomes and implementation lessons-learned will directly inform efforts to close race-ethnicity gaps in HIV treatment.

5.0 OBJECTIVES

5.1 Primary Objectives

The overarching goal of the CHOICES scale-up study is to determine the effectiveness of HIV clinic-based XR-NTX therapy in achieving HIV viral suppression in HIV-infected patients with opioid use disorder. Specific measures of study objectives outcomes are defined in Section 8.0.

Specific Aim: Compare HIV viral suppression (HIV-1 RNA \leq 200 copies/ml) among study participants randomized to XR-NTX versus TAU at 24 weeks from time of randomization.

5.2 Secondary Objectives

Secondary Specific Aims: Secondary aims compare the effectiveness of XR-NTX versus TAU in 1) other HIV outcomes (VACS Index, CD4 count), 2) engagement in HIV care (receipt of ART, ART adherence, retention in HIV care, HIV risk behaviors), and 3) ART adherence as mediated by number of opioid use days at 24 weeks. An additional secondary aim assesses barriers and facilitators of implementing XR-NTX for retaining patients in HIV primary care.

1) Secondary HIV Outcomes

- a. Change in VACS Index at 24 weeks, compared with randomization.
- b. Change in CD4 count at 24 weeks, compared with randomization.

2) Engagement in HIV Care:

- a. Proportion of participants prescribed ART within 24 weeks following randomization.
- b. Proportion of participants taking 100% of prescribed ART doses in the past month at 24 weeks for those prescribed ART at any point during the 24 week trial.
- c. Retention in HIV Care: Proportion of participants with at least 1 HIV primary care visit in the past 12 weeks, measured at week 24.
- d. HIV Risk Behaviors, as measured by the RAB at week 24.
- e. Quality of life as measured by EQ-5D at week 24, compared to baseline.

3) ART Adherence Mediation Variables:

- a. Number of days of opioid use since baseline, measured by Timeline Follow Back (TLFB) at 24 weeks.
- b. Past 30 day opioid abstinence (by Addiction Severity Index (ASI)-lite self-report, Timeline Follow Back (TLFB) and urine drug screen (UDS) confirmation at 24 weeks).

4) Assess barriers and facilitators of XR-NTX implementation to improve retention in HIV primary care:

Qualitative interviews with participants, providers, and staff to document the HIV primary care treatment environment and describe XR-NTX formative implementation strategies, challenges, and best practices.

6.0 STUDY DESIGN

6.1 Overview of Protocol Study Design

The CHOICES scale-up (CTN-0067) study is designed to compare the effectiveness of HIV clinic-based XR-NTX versus TAU in engaging HIV-infected persons with opioid use disorder in care to improve HIV viral suppression. The CTN-0067 CHOICES scale-up study builds on lessons learned from the pilot and uses the Consolidated Framework for Implementation Research [90] to advance understanding of XR-NTX adoption.

HIV clinics will serve as primary care clinic settings for CTN-0067. Eligible study sites must a) provide HIV primary care, b) have a sufficient population of potential participants to achieve study enrollment goals, c) have providers willing to be trained in use of XR-NTX for management of opioid use disorder, d) have the capacity to prescribe ART to participants, regardless of CD4 count, e) offer on-site addiction counseling services as part of usual care, and f) offer access to opioid agonist treatment, either on-site or by referral.

The CTN-0067 CHOICES scale-up study will utilize no more than 8 HIV primary care clinics to conduct the trial. The study is an open-label, randomized, comparative effectiveness implementation trial of office-based XR-NTX for 24 weeks (approximately 6 monthly injections) ($n = 175$) versus TAU ($n = 175$) in HIV-infected participants with untreated opioid use disorder (**Figure 1**).

In the pilot, 60 (85%) of 71 pre-screened individuals who reported using opioids in the past year said they were interested in stopping opioid use. Of these, 59 (98%) were willing to enroll in a clinical trial of XR-NTX for treatment of OUD, and 24 (41%) of those willing to try XR-NTX were randomized. Thus, 24 (34%) of 71 pre-screened individuals with past year illicit opioid use were ultimately randomized. Nine (38%) of these had an unsuppressed HIV viral load at baseline. Assuming the same proportion of pre-screened as randomized opioid users will be unsuppressed at prescreening, enrolling 350 participants in the scale-up may require pre-screening of about 2,709 [$350/(0.34*0.38)$] patients with past year opioid use.

The trial will be powered as a non-inferiority trial since the overall goal of the research is to add to rather than to supplant currently available effective opioid agonist treatment options. The *primary outcome* is the proportion of participants who achieve HIV viral suppression (HIV-1 RNA ≤ 200 copies/ml), measured at 24 weeks. *Secondary outcomes* include 1) other HIV outcomes (VACS Index, CD4 count), 2) engagement in HIV care (receipt of ART, ART adherence, retention in HIV care, HIV risk behaviors), and 3) ART adherence as mediated by number of opioid use days at 24 weeks. A fourth secondary objective documents facilitators and barriers of implementing XR-NTX to improve retention in HIV primary care (**Figure 1**).

6.2 Study Duration and Visit Schedule

The CTN-0067 CHOICES scale-up study will target enrolling 350 participants over approximately 22 months at no more than 8 HIV clinic sites. Each participant will be engaged in the overall study for an expected duration of 25-28 weeks (**Figure 3**) as follows:

- Weeks 1-4: consent, screening, randomization.
- 24 weeks: Active treatment with study visits every 4 weeks.
- Week 24: A single follow-up visit at the end of active treatment.

6.3 Justification of 24 weeks active treatment and timing of ART initiation

Assessment of the primary outcome of HIV viral suppression requires a minimum of 6 months, given the high potency of currently available ART regimens. While longer follow-up periods are required to assess sustained viral suppression, nearly all people initiating ART can now achieve an HIV viral RNA \leq 200 copies/mL within 6 months of ART initiation. Participants not already taking ART at study enrollment will be encouraged to begin ART as soon as possible following enrollment. The timing of XR-NTX initiation or ART initiation is up to the discretion of the HIV provider on the basis of the patient's clinical priorities. Finally, previous efficacy trials of XR-NTX for opioid use disorder [55] and alcohol use disorder [64] provided 24 weeks of XR-NTX.

6.4 Justification of Implementation Study Procedures

Overview. The HIV primary care treatment environment is likely to change during the course of the study, reflecting broader healthcare policy changes in society. Documenting the HIV primary care treatment environment and describing XR-NTX formative implementation strategies, challenges, and best practices is crucial both for interpreting study findings and advancing understanding of generalizability and sustainability in other settings. A mixed-methods implementation analysis of HIV providers, staff, administrators, and study participants enrolled in CTN-0067 assesses barriers and facilitators to the use of XR-NTX in participating HIV clinics. Results inform policy-making for dissemination of clinic-based XR-NTX to other settings.

Qualitative Interview Justification. Qualitative interviews provide critical detail for enhanced understanding of the findings from the comparative effectiveness trial (Secondary Aim). Using the Taxonomy of Mixed Method Designs [115-117], our design has a QUAN + qual structure with simultaneous data collection and emphasis/weight placed on the quantitative (comparative effectiveness trial) efforts. Recurrent themes extracted from key informant interviews document provider, organizational, and participant experiences over time to examine these findings in parallel with staff surveys and study participant outcomes data (i.e., HIV viral suppression). This approach is consistent with Type I hybrid implementation study designs recommended for comparative effectiveness trials [118]. HIV clinic characteristics and provider attitudes (inner setting), as well as detail about the use of XR-NTX (intervention characteristics), and community awareness, linkage across service settings, and policy support (outer setting) help identify the full range of complex variables associated with implementation of clinic-based XR-NTX. This approach represents an innovative strategy to integrate available quantitative study results (Secondary Aim) to examine the provider, patient, organizational, and policy-level changes that influence the uptake of XR-NTX in HIV clinics. Corresponding with the CFIR, we identify individual, organizational and contextual characteristics that influence uptake of XR-NTX. We will particularly explore barriers to XR-NTX adoption identified in substance abuse treatment center setting using a CFIR framework, such as cost, complexity of prescribing, health plan policies, and reluctance to change [91]. Mixed-methods including QUAN + qual data are well suited for studying implementation of clinic-based XR-NTX and assessing the influence of individual and organizational characteristics on utilization.

Data Collection and Management. Lead Node investigators will conduct audio-recorded key informant interviews with HIV clinic providers, staff and administrators (up to 60 total across sites) over the study period. A convenience sample of CTN-0067 study participants assigned to XR-NTX (up to 60 total across sites) will be approached by site research staff and consented for participation in qualitative interviews. Interview guides use the CFIR framework to probe participant perceptions of the characteristics of XR-NTX and TAU (e.g., intervention quality, advantage, adaptability), outer setting (e.g., resources, social support, social interactions, external policies and incentives), inner setting (e.g., clinic organization, networks and

communication, practice culture, and implementation climate), provider characteristics (e.g., self-efficacy for XR-NTX treatment) and the implementation process (e.g., engaging, executing, evaluating) [90, 119]. Not all questions will be asked of all informants.

Audio-recorded interviews will be professionally transcribed, reviewed and summarized. Transcriptions will be password protected, stored on a secure network and uploaded into qualitative analysis software (Atlas.ti™) which organizes data and facilitates coding and thematic analysis.

Qualitative data will be supplemented with a brief survey of participating sites ($n =$ no more than 8), completed prior to study initiation, to document local treatment environment (e.g., availability of clinic-based buprenorphine, state Medicaid support for medication-assisted treatment, amount of Ryan White Care Act funding, community referral resources, etc.).

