12.10 Treatment Initiation and XR-NTX Non-Initiation

The Treatment Initiation form will track participants randomized to the TAU arm only and will track initiation of TAU. This form will be completed once the participant reports that they have initiated TAU treatment. If treatment is not initiated, the form must be completed by end of study.

The XR-NTX Non-Initiation form will track non-initiation of XR-NTX injections for participants randomized to the XR-NTX treatment arm. This form will be completed as needed if a participant does not receive any XR-NTX injections. If the participant receives *at least* one injection, this form will not be completed.

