17.0 STATISTICAL ANALYSIS

17.1 Primary Objective of the Analysis

The Primary objective of the CTN-0067 CHOICES scale-up study is to discover whether HIV clinic-based XR-NTX is non-inferior to TAU with respect to HIV viral suppression in HIV-infected participants with opioid use disorder. We have chosen a non-inferiority margin of 0.75. That is, we will reject the null hypothesis of inferiority of XR-NTX to TAU in favor of non-inferiority if the lower 95% confidence limit for the ratio $\frac{\text{Pr}(\text{suppressed}|\text{NTX})}{\text{Pr}(\text{suppressed}|\text{TAU})}$ is strictly greater than 0.75. We anticipate a sample size of 350 (175/arm) will grant at least 80% power for the non-inferiority conclusion.

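### Participant interviews on XR-NTX barriers use a convenience sample, and nothing ensures that those who did not start, or who stopped, are heard

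*Combined protocol and SAP*

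**What the plan says.** Secondary objective 4 in section 5.2 is to "Assess barriers and facilitators of XR-NTX implementation to improve retention in HIV primary care". Section 6.4 describes the work: "A mixed-methods implementation analysis of HIV providers, staff, administrators, and study participants enrolled in CTN-0067 assesses barriers and facilitators to the use of XR-NTX". Its justification of the qualitative interviews adds that the analysis should identify what influences uptake.

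There are two sets of interviews. For clinics: "Lead Node investigators will conduct audio-recorded key informant interviews with HIV clinic providers, staff and administrators (up to 60 total across sites" (section 6.4). For participants: "A convenience sample of CTN-0067 study participants assigned to XR-NTX (up to 60 total across sites) will be approached by site research staff". Section 6.4 also plans a short site survey, completed before the study opens, and refers to staff surveys. Section 17.9 describes coding and triangulation of site, staff and patient material. Neither section gives a quota, a stratum or any rule tied to whether the interviewee started or stayed on XR-NTX.

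On starting treatment, section 4.3 reports from the pilot: "Five of 12 (42%) participants with any OUD assigned to XR-NTX initiated XR-NTX within 4 weeks of randomization". Section 12.10 provides a record of those who receive no injection: "The XR-NTX Non-Initiation form will track non-initiation of XR-NTX injections for participants randomized to the XR-NTX treatment arm".

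**The concern.** A question about uptake needs evidence from people who did not take the treatment up, and a question about retention needs evidence from people who left it. Convenience selection by site staff leaves both to chance. Participants who start have additional clinic contacts (the initiation visit, the safety visit and the injections themselves), so they may be easier to approach and more willing to talk.

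If the interviews tilt that way, difficulties with detoxification and induction would be described mostly by participants whom they did not stop. Section 6.4 regards this work as important for interpreting the trial and for policy on wider use, so a tilted sample could mislead on the step where the pilot lost most participants with OUD. Once follow-up ends, missed interviews are hard to recover.

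**Working it through.** **Inputs from the documents**
- Pilot initiation among participants with OUD: 5 of 12 within 4 weeks (section 4.3).
- Pilot initiation among all participants assigned to XR-NTX, opioid and alcohol use disorder together: 68% (section 4.3).
- XR-NTX arm: 175 (section 17.1).
- Participant interviews: at most 60, at no more than 8 sites (section 6.4).

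**Assumed, not in the documents:** r, the chance that a non-starter is interviewed relative to a starter. I show 1, 0.5, 0.25 and 0.1.

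**Step 1: reproduce the pilot figure.** 5/12 = 0.417, which rounds to the stated 42%. The complement is 7/12 = 58.3%. The exact (Clopper-Pearson) 95% interval for initiation is 15% to 72%.

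**Step 2: non-starters in the arm.** 175 × (1 − p), where p is the initiation rate:
- p = 0.417: 102
- p = 0.68: 56
- p = 0.152 and 0.723 (interval limits): 148 and 48

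**Step 3: non-starters among the interviewees.** Share s = (1 − p)r / [(1 − p)r + p]; count = 60s. For example, with p = 0.417 and r = 0.25, 0.583 × 0.25 = 0.146, then 0.146 / (0.146 + 0.417) = 0.259, and 60 × 0.259 = 15.6.

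| Initiation rate p | r = 1 | r = 0.5 | r = 0.25 | r = 0.1 |
|---|---|---|---|---|
| 0.417 | 35.0 (58%) | 24.7 (41%) | 15.6 (26%) | 7.4 (12%) |
| 0.68 | 19.2 (32%) | 11.4 (19%) | 6.3 (11%) | 2.7 (4.5%) |

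At p = 0.68 and r = 0.25, 6.3 interviews over 8 sites is about 0.8 per site.

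**Step 4: would an equal three-way split (20 never started, 20 stopped, 20 continuing) be the remedy?** It fixes the never-started share at 20/60 = 33%. Setting s = 1/3 gives r = p / [2(1 − p)], which at p = 0.417 is 0.417 / 1.167 = 0.36. If r is above 0.36, the fixed split yields fewer non-starters than the convenience sample. At p = 0.68 it yields slightly more than equal sampling would (20 against 19.2). No single fixed split suits both rates.

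**Step 5: can other sources supply the missing account?**
- Clinic interviews give the clinic's view of why participants did not start.
- The site survey is finished before anyone is randomized, so it cannot observe non-initiation.
- The Non-Initiation form records that no injection was given. Section 12.10 does not say that it collects reasons, and section 17.9 does not use it.

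No other interview source is stated for participants' own reasons.

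**The case against.** The strongest reply is that the sampling frame is assignment to XR-NTX, not receipt of it. Non-starters are eligible, share the 4-weekly visits in section 10.1, are compensated for them (section 9.8) and are to be followed for the whole study (section 9.6). A reader might infer that the sample is bound to under-represent them; the documents do not support that, because they give no information on r. This stands.

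A reader might also infer that barriers are learned only from this sample, or that non-starters are the group that met them. Neither holds. Up to 60 clinic interviews also address barriers. Those section 6.4 singles out (cost, prescribing complexity, health plan policy and reluctance to change) lie largely with clinics and payers. Participants who completed detoxification can describe it too, and section 9.2.3.3 identifies missed injections as the main threat once treatment has begun.

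Nor can 58% be read as the share who will never start. It is 7 of 12 people at 4 weeks, whereas this trial allows initiation until week 20 (section 9.1.9) and modifies induction to raise the rate (section 4.3).

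Finally, this is a qualitative aim in a design that gives its weight to the quantitative trial, and the plan sets no standard of proportional representation. That limits the importance of the point. It does not supply the missing rule: the aim is to explain uptake, and whether non-starters are heard remains undetermined.

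**Conclusion.** The point holds as a gap in the sampling plan. Section 6.4 does not ensure that participants who did not start XR-NTX, or who started and stopped, are interviewed, although objective 4 and section 6.4 ask about barriers and uptake.

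The size of any shortfall is unknown. Over the values shown, non-starters could number from 35 down to 7 of 60 at 42% initiation, and from 19 down to 3 at 68%. That spread rests on the assumed r and on a small pilot.

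The number who will stop is also uncertain. All 5 pilot starters with OUD were retained at 16 weeks, while the two earlier trials cited in section 4.3 report 68% retention at 8 weeks and 57.9% at 24 weeks. The consequence is confined to a secondary qualitative aim. The change is worth making because it needs no additional interviews.

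**What to change.** In section 6.4, replace convenience selection with purposive sampling by XR-NTX status at the time of interview, keeping the cap of 60:
- **Groups:** not started by a stated time after the 28-day initiation target; started then stopped; continuing. A participant counts as not started at the interview date even if initiation follows later. Waiting for final never-started status, which is not settled until about week 20, would push these interviews to the end of follow-up.
- **Numbers:** set a minimum for the not-started group in advance. Let the other group sizes follow the numbers that occur; do not fix an equal three-way split.
- **Spread:** over sites and over the study period.
- **Classification:** from the injection CRF (section 15.4), the Administration Log, the Non-Initiation form and the End of Treatment form (section 12.8). The Administration Log is not captured in eClinical (section 10.1), so sites would have to supply it.
- **Reporting:** give interviewees by status, and say in section 17.9 how the Non-Initiation form will be used.

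The cost is some extra effort to reach participants who did not start or who stopped. They remain in study follow-up, and the interview needs only verbal consent (section 18.16).
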